## LIST OF ABBREVIATIONS AND DEFINITIONS OF TERMS

The following abbreviations and specialist terms are used in this study protocol.

Abbreviation or Specialist Term	Definition
BOR	best overall response
CTCAE v5.0	Common Terminology Criteria for Adverse Events Version 5.0
DCR	disease control rate
DOE	duration of response
ECG	electrocardiogram
ECOG	Eastern Cooperative Oncology Group
EOT	end of treatment
ICF	Informed Consent Form
MedDRA	Medical Dictionary for Regulatory Activities
MRI	magnetic resonance imaging
NCI	National cancer institute
NSCLC	Non-small cell lung cancer
ORR	objective response rate
OS	overall survival
PD	progressive disease
PD-1	programmed cell death protein 1
pDC	plasmacytoid dendritic cell
PD-L1	programmed cell death ligand 1
PFS	progression-free survival
PR	partial response
Q3W	every 3 weeks
RECIST	Response Evaluation Criteria in Solid Tumors
SAE	serious adverse event
SAP	statistical analysis plan
SOC	system organ class
SOP	standard operating procedure
TEAE	treatment-emergent adverse event
TL	target lesion
TLR9	Toll-like receptor 9
TTR	time to response

Abbreviation or Specialist Term	Definition
W1D1	Week 1 Day 1

## 1. OVERVIEW

The SAP is intended to be a comprehensive and detailed description of the statistical methods, timing of analyses and analysis presentation to be used for the study specified in protocol CMP-001-009, Amendment 5 Global.

### 1.1. Study Description and Objectives

This is a phase 2 study to investigate intratumoral vidutolimod in combination with intravenous cemiplimab in subjects with selected types of advanced or metastatic cancer.

#### 1.1.1. Primary Objective

The primary objective of this study is to determine the confirmed ORR with vidutolimod in combination with cemiplimab.

#### 1.1.2. Secondary Objective(s)

The secondary objectives of the study are to:

- Evaluate the safety and tolerability of vidutolimod administered by IT injection in combination with cemiplimab
- Evaluate the efficacy of vidutolimod in combination with cemiplimab

#### 1.1.3. Exploratory Objectives

The exploratory objectives of this study are to:

- Evaluate the effect of vidutolimod in combination with cemiplimab on injected and noninjected target lesions
- To demonstrate treatment induced immune effects consistent with vidutolimod mechanism of action, including TLR9 signaling, increase in pDC activation, corresponding increase in CD8 T cell tumor infiltration, and activation status

## 1.2. Statistical Hypothesis

There is no formal statistical hypothesis for the study; the analyses of this study will be descriptive and exploratory in nature.

### 1.3. Interim Analysis(es)

There is no formal interim analysis in this study.

### 1.4. Modifications from the Statistical Section in the Final Protocol

None.

### 1.5. Revision History for SAP Amendments

This is the original version of the SAP .

## 2. INVESTIGATION PLAN

### 2.1. Study Design

This is a multicenter, open-label, Phase 2 clinical study of vidutolimod administered by IT injection in combination with cemiplimab IV in subjects with selected types of advanced or metastatic cancer with or without prior PD-1-blocking antibody treatment, as follows:

- Cohorts A1 and A2: Subjects with metastatic or locally and/or regionally advanced unresectable cutaneous squamous cell carcinoma (CSCC):
  - Cohort A1: Subjects who had not received prior systemic therapy for CSCC and who are not eligible for curative radiation
  - Cohort A2: Subjects who have progressed while receiving a PD-1-blocking antibody or within 12 weeks of discontinuation
- Cohorts B1 and B2: Subjects with metastatic or locally and/or regionally advanced unresectable Merkel cell carcinoma (MCC):
  - Cohort B1: Subjects who had not received prior systemic therapy for MCC
  - Cohort B2: Subjects who have progressed while receiving a PD-1-blocking antibody or within 12 weeks of discontinuation
- Cohorts C1 and C2: Previously treated subjects with advanced or metastatic triple-negative breast cancer (TNBC). Subjects must have previously received treatment with sacituzumab govitecan (all TNBC patients), with trastuzumab deruxtecan (HER2-low subjects) and with PARP inhibitor (for BRCA) subjects:
  - Cohort C1: Subjects who had not received prior therapy with immune checkpoint inhibitors (iCPIs)
  - Cohort C2: Subjects who have progressed while receiving a PD-1-blocking antibody or within 12 weeks of discontinuation
- Cohort D: Subjects with metastatic or locally and/or regionally advanced unresectable basal cell carcinoma (BCC) who have not received prior hedgehog pathway inhibitor therapy or prior anti-PD-1/PD-L1 therapy and who do not wish to receive or who are not candidates for a hedgehog inhibitor.
- Cohort E (not conducted in Europe): Advanced non-small cell lung cancer (NSCLC) subjects (locally advanced who are not candidates for surgical resection or definitive chemoradiation or metastatic) whose tumors have high PD-L1 expression (Tumor Proportion Score [TPS]  $\geq 50\%$ ) based on a prior PD-L1 result as determined by College of American Pathologists (CAP)/Clinical Laboratory Improvement Amendments (CLIA) (or equivalently licensed) lab, with no EGFR, ALK or ROS1 aberrations, and who have not received prior anti-PD-1/PD-L1 therapy and are amenable to IT therapy and do not wish to receive chemotherapy.
- Cohort F: Recurrent/metastatic (R/M) Oropharynx Squamous Cell Carcinoma (OPSCC) subjects with PD-L1 combined positive score (CPS)  $\geq 1$ , human papillomavirus (HPV)-positive disease who have not received prior systemic therapy for R/M disease. Human papillomavirus-positive status, based on a prior result, must be established in a surgical specimen or a core biopsy specimen from any site of OPSCC (primary site, nodal site, and/or distant metastatic site, either at time of diagnosis or later) in a CAP/CLIA (or equivalently licensed) lab. PD-L1 expression (CPS  $\geq 1$ ) is based on a prior PD-L1 result as determined by CAP/CLIA (or equivalently licensed) lab. Vidutolimod 10 mg will be

administered weekly for 7 doses, after which it will be administered Q3W until the subject meets a condition for discontinuation of study treatment. The first dose of vidutolimod may be administered SC or by IT injection, at the discretion of the Investigator; all subsequent doses are planned to be administered IT. The initial 7 vidutolimod doses, administered on a weekly schedule, must be completed before moving on to the Q3W vidutolimod dosing schedule.

The PD-1-blocking antibody administered in this study is cemiplimab. Treatment with cemiplimab will be administered IV infusion over 30 minutes ( $\pm 10$  minutes) at Week 1 Day 1 (W1D1) and Q3W thereafter. Cemiplimab administration will occur after vidutolimod administration.

All subjects will receive vidutolimod and cemiplimab according to the treatment schedule up to 2 years or until a reason for treatment discontinuation is reached.

Disease status will be assessed by computed tomography (CT) or magnetic resonance imaging (MRI) and other appropriate measures beginning predose at Week 10 Day 1 (W10D1) and will be repeated every 9 weeks (e.g. W19D1, W28D1, etc.) while the subject is on treatment. All scans should be performed at least 2 weeks after the previous vidutolimod IT injection to prevent detection of injection-related pseudoprogression. Imaging should not be delayed for delays in treatment.

[figure not shown]
Objective responses will be assessed by the Investigator according to RECIST v1.1.

Subjects who discontinue study treatment should complete the end of treatment (EOT) visit. AEs and concomitant medications data will be collected until 100 days after the last dose of study drug (vidutolimod or cemiplimab) or until an alternative anticancer treatment is initiated, whichever occurs first, including at a 100-day safety follow-up visit.

Subjects who are posttreatment but have not met criteria for study discontinuation should remain on study for posttreatment follow-up (PTFU), which includes disease assessments every 3 months until discontinuation. Long-term survival follow-up (LTSFU) will be conducted every 3 months after the EOT visit or the last disease assessment date in PTFU.

At the end of the treatment period (2 years), the Sponsor will not continue to provide supplied study treatment to subjects/investigators unless the Sponsor chooses to extend the study. The investigator should ensure that the subjects receive appropriate standard of care to treat the condition under study.

**Figure 1: Vidutolimod Study Schema**

Abbreviations: 100DFU = 100-Day Follow-up; EOT = end of treatment; LTSFU = long-term survival follow-up; IT = intratumoral; PD-1 = programmed cell death protein 1; PTFU = posttreatment follow-up; Q3W = every 3 weeks; Q9W = every 9 weeks; Q12W = every 12 weeks; QW = every week; SC = subcutaneous.

Note: The first dose of vidutolimod may be administered by SC or IT injection, per Investigator discretion. All subsequent doses of vidutolimod are planned to be administered IT.

## 2.2. Sample Size and Power Considerations

This study is conducted as an exploratory trial. Each cohort of A1, A2, B1, B2, C1, C2D, E and F, will enroll approximately 25 subjects. The total number of subjects to be enrolled into this study is approximately 225. Based on historical data, the ORR of available treatment for each disease in Cohort is listed in [Table 1](#). If the observed ORRs in these Cohorts A1, A2, B1, B2, C1, C2, D, E and F are at least as listed in [Table 1](#), then the lower bound of 90% confidence interval of ORR is listed in the table below.

**Table 1: ORR of Available Treatment by Cohort**

Cohort	ORR of Available Treatment	Observed ORR $\geq$	Lower Bound of 90% Confidence Interval
A1	50%	72%	>50%
A2	<10%	24%	>10%
B1	50%	72%	>50%
B2	<10%	24%	>10%
C1	21%	40%	>21%
C2	<10%	24%	>10%
D	50%	72%	>50%
E	39%	60%	>39%
F	19%	40%	>21%

### **3. ANALYSIS SETS**

The following defines the set(s) of subjects whose data will be used for statistical analysis.

#### **3.1. Full Analysis Set (FAS)**

The full analysis set (FAS) includes all enrolled patients who received any study drug. Efficacy endpoints will be analyzed using the FAS.

#### **3.2. Safety Analysis Set (SAF)**

The safety analysis set (SAF) includes all enrolled patients who received any study drug. Treatment administration and all clinical safety variables will be analyzed using the SAF. The FAS and SAF are the same.

#### **4. GENERAL STATISTICAL ANALYSIS CONSIDERATIONS**

Unless otherwise stated, the following conventions will be applied when presenting summary level statistics for data.

For continuous variables, descriptive statistics will include the following information: the number of patients reflected in the calculation (n), mean, standard deviation, Q1, median, Q3, minimum, and maximum.

For categorical or ordinal data, frequencies and percentages will be displayed for each category.

All analyses will be done using SAS Version 9.4 or above.

## 5. PATIENT DISPOSITION

### 5.1. Screening Dispositions

The following will be provided for all patients who signed the informed consent form:

- The number of screened patients, i.e., patients who signed the screening informed consent form.
- The number of patients who are enrolled.
- The number of patients who screen-failed.
- Screen failure reasons for patients who screen-failed.

### 5.2. End of Treatment and End of Study Dispositions

The following will be provided based on the FAS for each cohort:

- The number of patients in each analysis set.
- The number of patients who discontinue study treatment, and the reasons for study treatment discontinuation.
- The number of patients who discontinue study, and the reasons for study discontinuation.

### 5.3. Protocol Deviations

Protocol deviations will be defined in a separate protocol deviation definition document and be recorded in a separate list including the deviation reasons. The important protocol deviations, such as violation of inclusion/exclusion criteria will be determined before database lock and be summarized for each cohort.

## 6. DEMOGRAPHICS AND BASELINE CHARACTERISTICS

### 6.1. Demographics

The following demographic variables will be summarized based on the FAS for each cohort:

- Age at screening (year)
- Age categories (<65, >=65)
- Sex (Male, Female)
- Ethnicity (Hispanic/Latino, Not Hispanic or Latino, Not reported)
- Race (American Indian/Alaskan Native, Asian, Black/African American, Native Hawaiian/Other Pacific Islander, White, Other, Not reported)
- Baseline Luteinizing Hormone (LH) (mIU/ml)
- Baseline Weight (kg)
- Baseline Height (cm)
- Baseline Body mass index (BMI) (kg/m^2)

### 6.2. Baseline Disease Characteristics

The following baseline/initial disease characteristics that are common to all cohorts will be summarized based on the FAS for each cohort.

*Baseline Characteristics.* ECOG Performance Status at baseline, PD-L1 Status at Baseline, Time since Initial Diagnosis of Primary Cancer to First Dose (Months), Disease Type at Enrollment, Tumor Burden at Baseline, Measurable Disease at Baseline, and other key baseline information will be summarized by cohort using descriptive statistics for the Safety Analysis Set and listed by subject.

*Cancer History.* Cancer history (TNM staging, i.e., tumor stage, nodal status, metastatic disease status, and other key information measured at time of diagnosis) will be summarized by cohort using descriptive statistics for the FAS and listed by subject.

*Prior Cancer Treatments.* The prior cancer related treatments will be summarized across patients by cohort using descriptive statistics for the FAS.

### 6.3. Medical History

Patient medical histories will be coded using the Medical Dictionary for Regulatory Activities (MedDRA®). The frequency and percentage of each medical history will be summarized by SOC and PT for each cohort using the FAS.

## 7. EFFICACY DATA

### 7.1. Description of Efficacy Data

All endpoints below will be assessed based on data reported by the investigators.

ORR is defined as the number of patients with a best overall response (BOR) of confirmed complete response (CR) or partial response (PR) divided by the total number of patients.

- Confirmation of CR or PR must occur during a subsequent evaluation at a timepoint of at least 4 weeks from the initial assessment of CR or PR.
- Best overall response of SD must have met the response SD criteria at least once  $\geq 56$  days (9 weeks for first tumor assessment –7 days window) from the first study treatment administration
- Patient(s) without baseline tumor assessment or with either unknown or missing BOR will be counted as non-responder(s).

DOR, defined as time from first confirmed response of CR or PR to first radiographic progression or death due to any cause for patients with confirmed CR or PR. In the absence of radiographic progression or death on or before the analysis cutoff date or the date of initiation of a further anti-cancer treatment, the DOR will be censored at the date of the last valid response assessment not showing progression performed on or prior to the analysis cutoff date or initiation of a further anti-cancer treatment, whichever is earlier.

DCR, defined as the percentage of patients with a BOR of CR, PR, or stable disease (SD).

TTR, defined as time from first study treatment administration to first confirmed response of CR or PR for patients with confirmed CR or PR.

PFS defined as time from the first study treatment administration to first radiographic progression or death due to any cause. The same censoring rule as DOR will be used.

OS defined as the time from first study treatment administration to death due to any cause. For patients who have not died, OS will be censored at the last date that patient is known to be alive.

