2.2.2. Secondary Endpoints

The secondary endpoints are as follows:

- AEs, SAEs, and AEs leading to discontinuation or death, and severity of AEs as assessed by the National Cancer Institute Common Terminology Criteria for Adverse Events Version 5.0 (CTCAE v5.0)
- DOR, defined as the time from date of first documented response (CR or PR) to date of documented PD, based on RECIST v1.1
- Response in injected and noninjected target lesions per RECIST v1.1
- PFS, defined as the time from date of first dose of study treatment to date of documented PD based on RECIST v1.1 or death, whichever occurs first

- Overall survival (OS), defined as the time from date of first dose of study treatment to date of death

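### SAP 7.1 counts only radiographic progression as a PFS or DOR event, so a skin progression documented only by caliper or photograph would be censored or counted late

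*SAP*

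**What the plan says.** **SAP 7.1.** The DOR definition reads "DOR, defined as time from first confirmed response of CR or PR to first radiographic progression or death due to any cause", and the PFS definition reads "PFS defined as time from the first study treatment administration to first radiographic progression or death due to any cause". Censoring applies "In the absence of radiographic progression or death on or before the analysis cutoff date" (or start of further anti-cancer treatment). The censoring date is the last valid response assessment that does not show progression, and PFS takes the same rule. ORR in the same section has no modality limit: "ORR is defined as the number of patients with a best overall response (BOR) of confirmed complete response (CR) or partial response (PR").

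**Protocol.** Section 2.2.2 gives "PFS, defined as the time from date of first dose of study treatment to date of documented PD based on RECIST v1.1 or death" and "DOR, defined as the time from date of first documented response (CR or PR) to date of documented PD, based on RECIST v1.1". Section 8.6.2 adds death to the DOR event and relies on objectively documented recurrence or PD. Section 8.6.3 bases PFS on RECIST v1.1 by the investigator. None of these limits the modality. For DOR, 8.6.2 leaves the censoring details to the SAP; for PFS, 8.6.3 lets the SAP add censoring rules. Neither hands over the event definition.

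**Declared changes.** SAP 1.4, headed "Modifications from the Statistical Section in the Final Protocol", lists none.

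**The concern.** The protocol gives the word radiographic a specific meaning. Section 6.2.1 accepts only contrast-enhanced CT and MRI under that name, while Section 6.2 and Table 1 footnote q list photography as a separate method. Inclusion criterion 1 sets the two against each other: CSCC, MCC and BCC subjects with no radiographically measurable disease may enter on a lesion of at least 10 mm documented by colour photograph. Appendix B treats caliper-measured, photographed skin lesions as measurable.

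A progression seen only in such lesions is therefore a valid RECIST v1.1 progression under the protocol but not a radiographic one under the SAP. Censoring a subject because a skin lesion grew is informative, and it pushes PFS and DOR upward on average. The rule is also lopsided: a photographed skin response can start the DOR clock, but its photographed loss does not stop it.

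**Working it through.** The plan states no figure for this point, so the check is a comparison of text followed by an illustration of size.

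**1. What happens to a photograph- or caliper-only PD**

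| Step | Protocol | SAP 7.1 as written |
|---|---|---|
| Is it an event? | Yes, at its own visit | No, because it is not CT/MRI |
| Censoring date | Not applicable | Last assessment not showing progression, so normally the visit before |
| New therapy starts next | No effect | Fixes the censoring |
| CT/MRI PD or death follows before new therapy or cutoff | No effect | Event, but late |

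**2. Whether later scans recover it.** Not reliably. Table 1 footnote q makes confirmatory imaging optional and waives end-of-treatment imaging after progression. Section 3.2 sends to posttreatment assessments those who stopped for reasons other than progression, and Section 6.6 ends those assessments at progression. Subjects treated beyond progression keep the schedule (3.2.1), so some would be counted late rather than lost.

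**3. Who is exposed.** Nine cohorts of about 25 give 9 × 25 = 225, the planned total. Cohorts A1, A2, B1, B2 and D give 5 × 25 = 125, and 125/225 = 56%. This is the number in cohorts that admit such subjects, not the number of such subjects.

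**4. Illustrative PFS shift.** All inputs except the assessment interval are assumed: exponential PFS with a median of 4 or 10 months, 15% of events are deaths, cutoff uniform over 12 to 36 months, and a share q of progressions that are photograph/caliper-only. Progression is detected at the next 63-day visit (the protocol's 9 weeks). Under the literal rule these subjects are censored at the previous visit, or half of them are counted 63 days later. Simulation with 400,000 subjects per scenario gives this rise in landmark PFS, in percentage points:

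| q | 4-month median, 6-month PFS: none recovered / half recovered | 10-month median, 12-month PFS: none recovered / half recovered |
|---|---|---|
| 5% | 1.20 / 1.02 | 1.39 / 0.84 |
| 10% | 2.43 / 2.13 | 2.75 / 1.68 |
| 20% | 5.06 / 4.26 | 5.81 / 3.46 |

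The protocol-rule values are 0.47 and 0.48. Letting later deaths count (12-month median survival after PD, half starting new therapy and staying censored) widens the overall ranges only slightly: 0.80 to 1.39, 1.65 to 2.75 and 3.28 to 5.81.

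A hand check for the none-recovered case: if h is the event probability per 63-day interval and k the number of scheduled visits before the landmark, the SAP estimate is about the protocol estimate × (1 − 0.85qh)^(−k).
- 4-month median (121.75 days): h = 1 − 2^(−63/121.75) = 0.301 and k = 2. At q = 10%, 0.467 × [(1 − 0.0256)^(−2) − 1] = 2.5 points.
- 10-month median (304.4 days): h = 0.134 and k = 5. At q = 10%, 0.479 × [(1 − 0.01136)^(−5) − 1] = 2.8 points.

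Both agree with the simulation.

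**5. One cohort of 25.** In 6,000 simulated cohorts per scenario at q = 10% (later deaths not counted), the SAP estimate was higher in 48–67%, unchanged in 29–52% and lower in 0.5–3.7%. The 95% half-width is 1.96 × √(0.48 × 0.52/25) = 19.6 points.

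**6. DOR example.** Ten subjects respond at W10. At W28 three have CT progression, two have photograph-only progression and five continue.
- Protocol: 18-week DOR rate = 5/10 = 0.50.
- Literal SAP, the two censored at W19: 5/8 = 0.625.
- If the photograph is also ignored in dating the censoring, so that both are censored at W28: 7/10 = 0.70.

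Two of five progressions is a 40% share, above the range in step 4. With one of five (20%), the literal SAP gives 5/9 = 0.556 against 0.50.

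**The case against.** The best counter-argument is that the word is loose drafting. SAP 7.1 opens by saying that all endpoints rest on investigator-reported data. SAP 2.1 mentions CT or MRI and other suitable measures, and SAP 1.4's declaration of no change suggests none was intended. The author may only have wanted to exclude clinical progression, which protocol 3.2 lists separately. Appendix B combines all lesions into one overall response, so a programmer using that field would already count a skin PD; censoring it would need a CT/MRI-only derivation that neither document describes. Scans are also scheduled every 9 weeks in every cohort and may catch some of these progressions.

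The benign intent is plausible and cannot be ruled out. But the line on investigator data says who assesses, not what counts, and no SAP sentence says that a photographed progression is an event. The mechanism is real if the text is followed.

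Two points on size stand. The 0.50 versus 0.625 example uses a 40% share and should not be taken as typical. The censoring date also depends on whether a photograph can show progression for that purpose; ignoring it gives 0.70, a larger gap in the same direction.

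It also stands that "the analyses of this study will be descriptive and exploratory in nature" (SAP 1.2), so no decision rule rests on PFS or DOR.

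**Conclusion.** The concern holds. As written, the SAP event is narrower than the protocol's, the change is undeclared, and in five cohorts it drops or delays valid progressions in a direction that favours the treatment on average. The size is unknown because the documents do not give the photograph/caliper-only share. Under the assumptions above the average rise in landmark PFS is about 0.8–1.4, 1.7–2.8 and 3.3–5.8 points at shares of 5, 10 and 20%. That is small against the imprecision of a cohort of 25, and in a single cohort the estimate may not move or may, rarely, fall. The primary ORR is untouched. It should be fixed because the event definition contradicts the protocol, not because it threatens the main result. Confidence is medium, since the author's intent may have been benign.

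**What to change.** In SAP 7.1, replace radiographic progression in the DOR definition, the PFS definition and the censoring sentence with PD per RECIST v1.1 (protocol Appendix B) as determined by the investigator. Do not add a list of modalities: Appendix B also admits chest x-ray, cytology and FDG-PET findings, and a list would risk a new omission. This wording still excludes purely clinical progression. If a CT/MRI-only event is really wanted, declare it in SAP 1.4 as a departure from protocol 8.6.2 and 8.6.3.

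The cost is three wording changes; the assessments are already collected. PFS and DOR may look slightly less favourable in the skin-cancer cohorts.
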